5.5 Criteria for Taking a Participant Off Protocol Therapy

Duration of therapy will depend on individual response, evidence of disease progression and tolerance. In the absence of treatment delays due to adverse event(s), treatment may continue until one of the following criteria applies:

- Disease progression
- Intercurrent illness that prevents further administration of treatment
- Pregnancy
- Unacceptable adverse event(s)
- Participant demonstrates an inability or unwillingness to comply with the oral medication regimen and/or documentation requirements
- Participant decides to withdraw from the protocol therapy
- General or specific changes in the participant's condition render the participant unacceptable for further treatment in the judgment of the treating investigator
- EXCEPTION: patients deriving clinical benefit from study treatment may continue on therapy at the discretion of the treating investigator to bridge to next treatment even if there is evidence of progressive disease

Participants will be removed from the protocol therapy when any of these criteria apply. The reason for removal from protocol therapy, and the date the participant was removed, must be documented in the case report form (CRF). Alternative care options will be discussed with the participant.

An ODQ Treatment Ended/Off Study Form will be filled out when a participant is removed from protocol therapy. This form can be found on the ODQ website or obtained from the ODQ registration staff.

In the event of unusual or life-threatening complications, treating investigators must notify the Overall PI, [name], as soon as possible, at [contact], DFCI [name].

5.6 **Duration of Follow Up**

Once participants have completed study treatment they will be followed until initiation of new therapy, or until death, whichever occurs first. After cycle 24, subjects remaining on investigational therapy will be seen every 3 months in clinic for as long as they remain on study treatment. Subjects who discontinue acalabrutinib/venetoclax because they are in CR/CRi with MRD-negativity will be followed as per the study calendars in section 10. In these subjects, if no relapse is detected after 48 cycles of therapy, they may return to follow-up with a local

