If any significant laboratory changes are observed within the first 24 hours after initiation of dosing, see Appendix E (Recommendations for Initial Management of Electrolyte Abnormalities and Prevention of Tumor Lysis Syndrome [TLS]), for additional laboratory assessments and management guidelines. If aggressive correction of electrolytes abnormalities was performed, the subsequent dose of venetoclax can only be given when electrolytes have been stable without any further treatment for approximately 24 hours.

^a Administer intravenous hydration for any patient who cannot tolerate oral hydration.

^b If possible start allopurinol or xanthine oxidase inhibitor about 3 days prior to initiation of venetoclax.

^c Evaluate blood chemistries (potassium, uric acid, phosphorus, calcium, and creatinine); review in real time. During the dose ramp-up period, the subsequent dose should not be administered until the 24 hours post-dose laboratory values are reviewed by the investigator.

 $^{^{\}rm d}$ All same-day laboratory assessments may be taken within ± 2 hour window, and 24 hour laboratory assessments within a ± 6 hour window, if necessary

 $^{^{\}rm c}$ Intravenous fluids should be given at 150-200 mL/hr starting the night before the first dose of 20 mg, with a target of approximately 1.5-2 L/day (or as clinically appropriate), and continued for at least 24 hours after completing the 50mg dose.

f Rasburicase (given at a flat dose of 6 mg IV x 1, or per institutional standards) should be administered per institutional guidelines for patients with elevated uric acid level at baseline (> ULN) as prophylaxis prior to the initial dose of venetoclax. For patients with a contraindication to rasburicase (i.e., glucose-6-phosphate dehydrogenase [G6PD] deficiency), the TLS risk-mitigation plan must be reviewed with the Overall PI.

Management of Other Toxicities

The following tables provide recommended guidelines for venetoclax dose reduction based on specific toxicities. Any subject who discontinues venetoclax due to toxicity may continue on the other study medications. Management not consistent with these guidelines should be discussed with the Overall PI:

Table 7: Dose Reduction Strategy for Patients Experiencing Non-Hematologic Toxicities on Venetoclax

Non-hematologic Toxicity Grade	Recommended Management/Next Dose for Venetoclax
≤ Grade 1 or 2	No change in dose

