Grade 3	Hold* until ≤ Grade 1. At first occurrence, resume at same dose, no dose modification is required. At second and subsequent occurrences,** hold venetoclax and follow dose reduction guidelines in Table 5 when resuming treatment with venetoclax after resolution.
Grade 4	Permanently cease venetoclax therapy unless toxicity can be attributed to an alternative cause

^{*}Participants requiring a hold of >4 weeks of venetoclax due to a toxicity thought to be related to venetoclax should go off venetoclax therapy unless approved by the overall PI to remain on therapy.

With regard to specific nonhematologic toxicities, the recommended management for venetoclax-associated diarrhea is loperamide, dosed at 4 mg at first onset, followed by 2 mg with each loose bowel movement until diarrhea-free for 12 hours (maximum dosage: 16 mg/24 hours). Adjunct anti-diarrheal therapy is permitted and should be recorded when used.

Table 8: Dose Reduction Strategy for Patients Experiencing Neutropenia on Venetoclax

Neutropenia in				
patients on	Recommended Management/Next Dose for Venetoclax			
venetoclax				
≤ Grade 1 or	No change in dose			
Grade 2				
Grade 3 (ANC 500-999 cells/mm³)	Hold* until \leq Grade 2 or continue at current dose as long as growth factor is administered. (If venetoclax is continued, repeat ANC within 3 days and if still grade \geq 3, hold venetoclax until \leq Grade 2.) If not previously growth factor responsive, resume at one dose level lower, if indicated.**			
Grade 4	$ \text{Hold}^* $ until \leq Grade 3, then resume therapy at the same dose but with G-CSF			
(ANC <500	support. On second and subsequent occurrences, follow dose reduction			
cells/mm ³)	guidelines in Table 5 when resuming treatment.**			

*Participants requiring a hold of >4 weeks of venetoclax due to a venetoclax related therapy should go off protocol therapy unless approved by the overall PI to remain on therapy.

^{**}Participants requiring >3 dose reductions of venetoclax should go off venetoclax unless approved by the overall PI to remain on therapy.

^{**}Participants requiring >3 dose reductions of venetoclax should go off venetoclax unless with approval by the overall PI to remain on therapy.

Neutropenia in	
patients on	Recommended Management/Next Dose for Venetoclax
venetoclax	

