At any time during the study, if the patient presents with febrile neutropenia, it is recommended that venetoclax be interrupted until resolution of the fever or infection. At the first occurrence, venetoclax may then be re-initiated at the same dose. At a second or later occurrence, consideration should be given to venetoclax dose reduction.

Growth factor support with filgrastim or pegfilgrastim may be utilized as necessary throughout the study and does not require holding venetoclax.

Table 9: Dose Reduction Strategy for Patients Experiencing Venetoclax-Related Hematologic Toxicities (excluding Neutropenia)

Venetoclax-related Hematologic Toxicities	Management/Next Dose for Venetoclax
\leq Grade 1, 2, or 3	No change in dose
Grade 4	Hold* until \leq Grade 3, unless the toxicity is thought to be due to a cause other than venetoclax. On first occurrence, venetoclax may be resumed at the same dose. On second and subsequent occurrences, follow the dose reduction guidelines in Table 5.**

*Participants requiring a hold of >4 weeks of venetoclax due to a venetoclax related therapy should go off protocol therapy unless approved by the overall PI to remain on therapy.

**Participants requiring >3 dose reductions of venetoclax should go off venetoclax unless with approval by the overall PI to remain on therapy.

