6.2 Obinutuzumab

Dose Reduction Table

The dose of obinutuzumab is not modified but doses can be held or delayed as needed. Dose delays of obinutuzumab may be made as per the tables below if a toxicity is believed to be at least likely related to obinutuzumab. If a subject must permanently discontinue obinuzutumab prior to completion of the full six month course, acalabrutinib and venetoclax will continue to be administered as per the study calendar detailed in section 10. For the adverse event profile, see section 7.1.1 and the obinutuzumab IB.

Table 10: Dose Modifications for Non-Infusion-Related-Reaction, Non-Hematologic Toxicities

Worst CTCAE Grade Toxicity	Recommended Action to be Taken
Grade 1 or 2	None
Grade 3 CTCAE	Hold dosing of obinutuzumab until toxicity Grade ≤2
If toxicity remains grade 3 toxicity for longer than 2 weeks	Consider permanent discontinuation of obinutuzumab
Recurrence of Grade 3 toxicity	Consider permanent discontinuation of obinutuzumab
Grade 4 CTCAE	Hold dosing of obinutuzumab until toxicity resolves to Grade ≤2
Recurrence of Grade 4 toxicity	Consider permanent discontinuation of obinutuzumab

Infusion Related Reactions

If a patient experiences any grade infusion reaction during infusion, adjust the infusion as outlined below:

- Grade 4 (life-threatening): Stop infusion and permanently discontinue therapy.
- Grade 3 (severe): Temporarily interrupt infusion and treat symptoms. Upon resolution of symptoms, restart infusion at no more than half the previous rate (the rate being used at the time that the infusion reaction occurred) and, if patient does not experience any infusion reaction symptoms, infusion rate escalation may resume at the increments and intervals as appropriate for the treatment dose. The Day 1 infusion rate may be increased back up to 25 mg/hr after 1 hour but not increased further. Consideration can be given to following a desensitization protocol for future administration of the antibody.
- Grade 1-2 (mild to moderate): Reduce infusion rate and treat symptoms. Upon resolution of symptoms, continue infusion and, if patient does not experience any infusion reaction symptoms, infusion rate escalation may resume at the increments and intervals as appropriate for the treatment dose. The Day 1 infusion rate may be increased back up to 25 mg/hr after 1 hour but not increased further.

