6.3 Acalabrutinib

Treatment with acalabrutinib should be held for any unmanageable, potentially study drug-

related toxicity that is Grade ≥ 3 in severity. Study drug may be held for a maximum of 28 consecutive days from expected dose due to toxicity. Acalabrutinib should be permanently discontinued in the event of a toxicity thought at least possibly due to acalabrutinib lasting > 28 days despite holding drug, unless reviewed and approved by the Overall PI. Any subject who permanently discontinues acalabrutinib prior to cycle 4 will no longer be eligible for any of the study drugs and will come off study treatment but continue to be followed as detailed in section 5.6. Any subject who discontinues acalabrutinib at cycle 4 or later may continue on the other study medications.

Dose Reduction Table

The actions in Table 11 below should be taken for the following toxicities if thought to be at least possibly related to acalabrutinib:

- Grade 4 ANC ($< 500/\mu$ L) for > 7 days (Neutrophil growth factors are permitted and use must be recorded on the case report form [CRF]).
- Grade 3 or higher platelet decreases in presence of significant bleeding.
- Grade 4 platelet decreases.
- Grade 3 or 4 nausea, vomiting, or diarrhea, if persistent for >7 days despite optimal antiemetic and/or anti-diarrheal therapy.
- Any other Grade 4 toxicity or unmanageable Grade 3 toxicity.

Table 11: Dose Modifications for Acalabrutinib

Occurrence	Action
1st - 2nd	Hold acalabrutinib until recovery to Grade ≤ 1 or baseline; may restart at
	original dose level
3rd	Hold acalabrutinib until recovery to Grade ≤ 1 or baseline; restart at one dose
	level lower (100 mg once daily)
4th	Discontinue acalabrutinib

Any changes to the dosing regimen must be recorded in the Dosage Administration CRF.

If acalabrutinib is reduced for apparent treatment-related toxicity, the dose need not be re-escalated, even if there is minimal or no toxicity with the reduced dose. However, if the subject tolerates a reduced dose of acalabrutinib for ≥ 4 weeks then the dose may be increased to the next higher dose level, at the discretion of the investigator. Such re-escalation may be particularly warranted if further evaluation reveals that the AE that led to the dose reduction was not treatment-related.

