6.4 Integrated Toxicity Management Guidelines When the Causative Agent is Unclear

The study drugs have some overlapping toxicities (e.g. diarrhea with venetoclax and acalabrutinib, neutropenia with all three agents), and in certain instances it may be unclear which agent is responsible for an adverse event that a patient is experiencing. If the treating clinician can identify the specific drug causing an adverse event, then the guidelines in sections 6.1-6.3 can be used to guide dose reductions of that individual drug. If, however, the treating clinician is

uncertain which agent is responsible for a particular adverse event, then the guidelines below should be used for management of study drug dosing in these circumstances:

For grade 1 or grade 2 toxicities where the causative drug is uncertain, no changes to study drug dosing need to be made.

For grade 3 or 4 hematologic and non-hematologic toxicities where the causative drug is uncertain, all suspected drugs should be held until the toxicity improves. One drug (at treating clinician discretion) should then be introduced (at the same dose as when the medication was discontinued). Of note, if one of the suspected causes is obinutuzumab, the other suspected agent(s) (with a shorter half-life) should be introduced first. If the toxicity recurs after reintroduction of the first drug, then the adverse effect is deemed attributable to this drug and management should proceed according to the guidelines in sections 6.1-6.3. The other suspected agents may then be reintroduced after the toxicity has improved. If, on the other hand, the toxicity does not occur after one week of therapy with the first drug, a second study drug should be reintroduced. If the toxicity occurs, then the adverse effect is deemed attributable to this second drug and management should proceed according to guidelines in sections 6.1-6.3. If a third study drug is also suspected, then it may be introduced one week later if no toxicity has been observed after introduction of the first two.

During cycle 8 and beyond, patients who have to hold either acalabrutinib or venetoclax due to drug-specific toxicity for longer than 4 weeks may stay on study and continue on monotherapy with the other agent that is not believed to be responsible for that toxicity.

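### Tables 8 and 9 take a patient off all protocol therapy by default after a venetoclax hold of more than 4 weeks, whereas Table 7, the section 6.1 text and section 6.4 stop venetoclax only (minor inconsistency)

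*Combined protocol and SAP*

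**What the plan says.** Section 6.1 (Management of Other Toxicities) introduces three tables for venetoclax: Table 7 for non-hematologic toxicity, Table 8 for neutropenia and Table 9 for other hematologic toxicity. The introduction calls them recommended guidelines and asks that departures be discussed with the Overall PI. It also states: "Any subject who discontinues venetoclax due to toxicity may continue on the other study medications". That sentence carries no limit by cycle or type of toxicity.

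Each table has a single-asterisk footnote for long holds and a double-asterisk footnote for repeated dose reductions. Under Tables 8 and 9 the long-hold footnote begins "Participants requiring a hold of >4 weeks of venetoclax due to a venetoclax related therapy", and its cause and consequence together read "due to a venetoclax related therapy should go off protocol therapy unless approved by the overall PI to remain on therapy". The double-asterisk footnote of the same two tables says: "Participants requiring >3 dose reductions of venetoclax should go off venetoclax unless with approval by the overall PI to remain on therapy". Under Table 7 the long-hold footnote refers to a toxicity thought to be related to venetoclax and withdraws venetoclax only.

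The last paragraph of section 6.4 covers the same length of hold later in treatment: "During cycle 8 and beyond, patients who have to hold either acalabrutinib or venetoclax due to drug-specific toxicity for longer than 4 weeks". Those patients may remain on study and take the other agent alone.

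**The concern.** The same event, a venetoclax hold of more than 4 weeks for a toxicity attributed to venetoclax, has opposite defaults in neighbouring parts of the dosing section. Under Tables 8 and 9 the patient leaves the whole regimen unless the PI steps in. Under Table 7, the section 6.1 introduction and section 6.4, only venetoclax stops.

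This is an instruction on treatment, not background text. Followed literally, it withdraws acalabrutinib, and obinutuzumab if any doses remain, because of a cytopenia attributed to a different drug. It would also change bookkeeping: section 13.6 plans to report discontinuation by reason and for individual components, and a whole-regimen removal is counted differently from a venetoclax-only stop.

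**Working it through.** The plan gives no figure on this point, so the check is a comparison of texts.

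**Step 1. The six footnotes in section 6.1.**

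| Table | Hold of more than 4 weeks (*) | More than 3 dose reductions (**) |
|---|---|---|
| 7, non-hematologic | off venetoclax | off venetoclax |
| 8, neutropenia | off protocol therapy | off venetoclax |
| 9, other hematologic | off protocol therapy | off venetoclax |

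Four of the six withdraw venetoclax only, and two withdraw protocol therapy (4 + 2 = 6). Within Tables 8 and 9, a long hold ends everything while repeated dose reductions end only venetoclax. No reason is given for the difference.

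**Step 2. What protocol therapy means.** Section 5.5 uses the term for treatment as a whole and attaches an administrative step: "An ODQ Treatment Ended/Off Study Form will be filled out when a participant is removed from protocol therapy". Section 6.1 itself separates it from venetoclax therapy. Reading it as the whole regimen is an inference, but both places support it.

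**Step 3. Which other rules reach the same patient.** Venetoclax starts in cycle 4.
- Cycles 4 to 7: the section 6.1 introduction applies. It is permissive and speaks of discontinuing venetoclax.
- Cycle 8 onward: section 6.4 applies as well, with the same trigger of more than 4 weeks. Its heading concerns an unclear causative agent, but this sentence is about drug-specific toxicity and does not exclude hematologic events.

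Neither rule makes continuing the other drugs depend on PI approval.

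**Step 4. Error or choice?** Three features point to an error.
- The Table 8 and 9 footnotes speak of a venetoclax-related *therapy* as the cause of the hold. Only *toxicity* makes sense, and Table 7 has it right.
- The rules for the other two drugs keep the rest of the regimen going. For obinutuzumab (section 6.2): "If a subject must permanently discontinue obinuzutumab prior to completion of the full six month course, acalabrutinib and venetoclax will continue to be administered". For acalabrutinib (section 6.3): "Any subject who discontinues acalabrutinib at cycle 4 or later may continue on the other study medications".
- Where the protocol does want every drug stopped, it says so outright: section 6.3 bars a patient who permanently stops acalabrutinib before cycle 4 from all study drugs.

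**The case against.** The strongest defence is that little can go wrong in practice. The tables are recommendations. A site that kept acalabrutinib going against the footnote would be departing from the table, and section 6.1 sends that site to the Overall PI, the same person the footnote names. One central decision-maker makes divergent handling unlikely. This stands, and it is the main reason the point is minor. A reader might infer that sites will treat identical patients differently. The text leaves room for that, but the referral to the PI means the documents do not show it to be likely.

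It can also be said that a specific footnote using *should* overrides a general sentence using *may*. That is arguable for cycles 4 to 7. It does not work from cycle 8, because section 6.4 names the same length of hold and is at least as specific.

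The footnote may also rarely be reached. Table 8 lets venetoclax continue through Grade 3 neutropenia with growth factor, and requires a hold only if a repeat count within 3 days is still Grade 3 or worse. If the cytopenia is also possibly due to acalabrutinib, section 6.3 has its own hold and stopping rules. Both points stand. For the same reason the contrast cannot be tied to a particular band of neutrophil or platelet counts by way of the section 5.2 cycle-start criteria. Those apply only if labs are checked before a cycle, and they delay treatment without ending it.

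Finally, a reader might infer that affected patients drop out of follow-up or of the primary analysis. The documents say otherwise. Toxicity is not among the off-study criteria in section 5.7, section 5.6 keeps such patients in follow-up, and section 13.7 counts everyone who received at least one dose as evaluable.

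**Conclusion.** The inconsistency is real and minor. Two of the six footnotes under Tables 7 to 9 give a default that contradicts their counterparts, the paragraph introducing them and, from cycle 8, section 6.4. The wording suggests a drafting error.

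The number of patients affected cannot be derived from the documents and may be zero. Neutropenia of Grade 3 or higher is common (52.8% with venetoclax plus obinutuzumab in the phase 3 trial described in section 2.2.1.14), but no rate of holds beyond 4 weeks is given. Section 2.2.1.12 reports that no patient in the phase 2 venetoclax study in 17p-deleted disease had to stop permanently for neutropenia. No effect on the primary endpoint, the sample size or any error rate is claimed.

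The conclusion rests on two readings: that protocol therapy means the whole regimen, and that *therapy* in the two footnotes is a slip for *toxicity*. If a whole-regimen stop were in fact intended for prolonged hematologic toxicity, the introduction to section 6.1 and the last paragraph of section 6.4 would need an explicit exception.

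**What to change.** Under Tables 8 and 9, replace the single-asterisk footnote with the one under Table 7, word for word. The cause of the hold then becomes a toxicity thought to be related to venetoclax, and the consequence becomes going off venetoclax therapy unless the Overall PI approves remaining on it. No further clause is needed, because the introduction to section 6.1 already lets the other drugs continue.

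The cost is one sentence in two footnotes at the next amendment, with a short memo to sites. There are no new procedures, visits or patients.

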6.2 Obinutuzumab

Dose Reduction Table

The dose of obinutuzumab is not modified but doses can be held or delayed as needed. Dose delays of obinutuzumab may be made as per the tables below if a toxicity is believed to be at least likely related to obinutuzumab. If a subject must permanently discontinue obinuzutumab prior to completion of the full six month course, acalabrutinib and venetoclax will continue to be administered as per the study calendar detailed in section 10. For the adverse event profile, see section 7.1.1 and the obinutuzumab IB.

Table 10: Dose Modifications for Non-Infusion-Related-Reaction, Non-Hematologic Toxicities

Worst CTCAE Grade Toxicity	Recommended Action to be Taken
Grade 1 or 2	None
Grade 3 CTCAE	Hold dosing of obinutuzumab until toxicity Grade ≤2
If toxicity remains grade 3 toxicity for longer than 2 weeks	Consider permanent discontinuation of obinutuzumab
Recurrence of Grade 3 toxicity	Consider permanent discontinuation of obinutuzumab
Grade 4 CTCAE	Hold dosing of obinutuzumab until toxicity resolves to Grade ≤2
Recurrence of Grade 4 toxicity	Consider permanent discontinuation of obinutuzumab

Infusion Related Reactions

If a patient experiences any grade infusion reaction during infusion, adjust the infusion as outlined below:

- Grade 4 (life-threatening): Stop infusion and permanently discontinue therapy.
- Grade 3 (severe): Temporarily interrupt infusion and treat symptoms. Upon resolution of symptoms, restart infusion at no more than half the previous rate (the rate being used at the time that the infusion reaction occurred) and, if patient does not experience any infusion reaction symptoms, infusion rate escalation may resume at the increments and intervals as appropriate for the treatment dose. The Day 1 infusion rate may be increased back up to 25 mg/hr after 1 hour but not increased further. Consideration can be given to following a desensitization protocol for future administration of the antibody.
- Grade 1-2 (mild to moderate): Reduce infusion rate and treat symptoms. Upon resolution of symptoms, continue infusion and, if patient does not experience any infusion reaction symptoms, infusion rate escalation may resume at the increments and intervals as appropriate for the treatment dose. The Day 1 infusion rate may be increased back up to 25 mg/hr after 1 hour but not increased further.

Hypotension may be expected to occur during obinutuzumab infusions. Withholding of antihypertensive treatments should be considered for 12 hours prior to and throughout each obinutuzumab infusion and for the first hour after administration. Patients at acute risk of hypertensive crisis should be evaluated for the benefits and risks of withholding their hypertensive medication.

Tumor Lysis Syndrome

Management of tumor lysis syndrome related to obinutuzumab should be managed as per standard of care. Subjects should be monitored for TLS after the first infusion of obinutuzumab on cycle 2 day 1 as outlined in the study calendar in section 10.

